6.1. Statistical Plan

6.1.1. Sample Size Determination

Sample size is based on a possible reduction in risk of neonatal mortality/BDP in infants at 36 weeks PMA receiving the SI intervention compared to those who receive the standard PEEP/CPAP. The significance level was set at $\alpha=0.038$ (due to the interim analyses), and power at 80%. Based on information from the recent multi-center NICHD SUPPORT trial² and the COIN trial,²⁰ we estimate that the baseline rate of neonatal mortality/BDP in the standard or care (control) arm by 36 weeks is 65%.

In order to detect an absolute risk reduction of 12.5%, 263 subjects per treatment arm are required. We anticipate virtually no loss to follow-up for the primary endpoint as infants will likely still be hospitalized because of their condition, will be under constant and continuing medical care. We have inflated the estimate by 1.12 to allow for twins and multiples to be randomized together. With this inflation in mind, the target sample size for this study is 300 subjects per arm.

For the secondary outcomes available in all subjects, with 263 subjects per arm (ignoring the twin correction factor), there will be 80% power to detect a difference of 0.24 standard deviation units in continuous outcomes, and a hazard ratio of 0.77 in survival outcomes under a proportional hazards assumption. Some secondary outcomes will not be available due to death of the infant, or loss to follow-up after discharge from the NICU. Overestimating these rates at 50%, we assume 130 subjects per arm will be available for the longer term secondary outcomes. With this sample size we will still have sufficient power to detect a clinically meaningful difference of at least 17% in event rates (or odds ratio of at least 2.0).

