6.2. Interim Analysis

Since neonatal safety is a consideration in this study, we have chosen to use a group sequential design. Thus, in addition to the final analysis, we are planning on performing two interim statistical analyses during the course of this study. The purpose of the interim analyses will be to determine whether or not there is sufficient evidence of a difference between the treatment arms in the primary endpoint such that the trial should be discontinued prior to reaching the target accrual goal. The interim analyses will be performed after approximately 1/3 (200 subjects) and 2/3 (400 subjects) of the total required patients have completed their primary outcome. An additional safety review will be undertaken after 1/6 (100 subjects) have completed their primary outcome.

The primary outcome for the interim analyses will be the comparison of death/BPD between the treatment arms. This comparison will be accomplished by means of a simple generalized estimating equation (GEE) model for death/BPD versus treatment (since adjustment for multiples will be needed). An approximate O'Brien-Fleming boundary will be used at each interim look to calculate the nominal significance level to which interim p-values are compared.²² Using the O'Brien Fleming spending function, the three analyses (2 interim + final) should use the following incremental α values (0.0002, 0.012, and 0.038) in order to achieve an overall $\alpha=0.05$.

Stopping criteria are for:

(1) Clear superiority. Whether the experimental treatment is clearly inferior to standard therapy. For these calculations, we trade off the power to detect a difference and the size of that difference. Assuming $\alpha=0.0002$ for boundaries for the initial interim analysis when 200 children have been followed to completion, power is limited except to detect large reductions in outcomes of death and BPD. For example, power is approximately 0.81 to detect a reduction from 65% in the conventional therapy to

32.5% in the experimental therapy, a 50% relative reduction. For the second interim analysis, using $\alpha=0.012$, power with 400 children followed is about 0.85 to detect an absolute reduction from 65% to 40% in the risk of death plus BPD. Thus, early or premature stopping for superiority is unlikely, without dramatic improvement from experimental treatment.

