(2) Inferiority. Power is limited to identify inferiority of the experimental treatment, with 0.8 power to demonstrate a 15% point increase in the risk of outcome from 65% in the standard therapy to 80% in the intervention.

(3) Futility. Early stopping based on futility of the primary outcome will not be considered independently of the secondary clinical and safety outcomes. In the event that the intervention arm has equivalent BPD/death rates to the standard care arm, it would still be clinically useful to know if the intervention improves any of the secondary outcomes (that are closer to the time of the intervention) or decreases the serious adverse event rate.

(4) Safety.

(a) Early stopping based on inferior safety and non-inferior efficacy must be based largely on descriptive data and close examination of adverse events. With 200 subjects per group at a second early stopping review, and assuming that the experimental therapy is actually no worse than conventional care, observed risk in the experimental group would have to be at most 0.5 (risk of death and BPD) to have 80% power to show non-inferior efficacy (with $\alpha = 0.012$).

(b) To justify stopping for non-inferior efficacy and superior safety again will require a substantial observed improvement in the experimental arm at the second early stopping time.

(c) Another safety outcome is the rate of pneumothorax, pulmonary interstitial emphysema (PIE), and/or other serious adverse events (that have been adjudicated as potentially relating to the intervention; see section 8.2.2). In order to minimize the risk, this safety outcome will be compared between treatment arms after 1/6 (100 subjects) have completed the primary outcome, as well as at the two planned interim analyses for the primary outcome (1/3 and 2/3), since we would not expect any statistically significant differences in the rate after 100 subjects (with O'Brien-Fleming $\alpha 0.000002$). Instead, we will look for a clinically meaningful double the risk in the intervention versus standard care arms.

In summary, given the projected number of patients to be enrolled, early stopping will be unlikely unless the observed effect of experimental care is clearly better or worse than standard care at the planned early stopping assessment times.

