- (1) Clear superiority -- whether the experimental treatment is clearly inferior to standard therapy. For these calculations, we trade off the power to detect a difference and the size of that difference. Assuming α =0.0002 for boundaries for the initial interim analysis when 200 children have been followed to completion, power is limited except to detect large reductions in outcomes of death and BPD. For example, power is approximately 0.81 to detect a reduction from 65% in the conventional therapy to 32.5% in the experimental therapy, a 50% relative reduction. For the second interim analysis, using α =0.012, power with 400 children followed is about 0.85 to detect an absolute reduction from 65% to 40% in the risk of death plus BPD. Thus, early or premature stopping for superiority is unlikely, without dramatic improvement from experimental treatment.
- (2) Futility. Early stopping based on futility of the primary outcome will not be considered independently of the secondary clinical and safety outcomes. In the event that the intervention arm has equivalent BPD/death rates to the standard care arm, it would still be clinically useful to know if the intervention improves any of the secondary outcomes (that are closer to the time of the intervention) or decreases the serious adverse event rate.
- (3) Inferiority. Power is limited to identify inferiority of the experimental treatment, with 0.8 power to demonstrate a 15% point increase in the risk of outcome from 65% in the standard therapy to 80% in the intervention.

(4) Safety.

- (a) Early stopping based on inferior safety and non-inferior efficacy must be based largely on descriptive data and close examination of adverse events. With 200 subjects per group at a second early stopping review, and assuming that the experimental therapy is actually no worse than conventional care, observed risk in the experimental group would have to be at most 0.5 (risk of death and BPD) to have 80% power to show non-inferior efficacy (with alpha = 0.012).
- (b) To justify stopping for non-inferior efficacy and superior safety again will require a substantial observed improvement in the experimental arm at the second early stopping time.

In summary, given the projected number of patients to be enrolled, early stopping will be unlikely unless the observed effect of experimental care is clearly better or worse than standard care at the planned early stopping assessment times.

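### The 0.8 power to show harm names no look or alpha: of the two interim looks it fits only the second, ignoring multiples (about 0.75 with the plan's 1.12 factor), and at the first look it is 0.07 to 0.09

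*Protocol*

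**What the plan says.** Protocol 6.2, item (2), says the trial has limited power for inferiority, "with 0.8 power to demonstrate a 15% point increase in the risk of outcome from 65% in the standard therapy to 80" per cent. SAP section 4, item (3), repeats this: "Power is limited to identify inferiority of the experimental treatment, with 0.8 power to demonstrate a 15% point increase in the risk of outcome". Neither sentence gives a look, a sample size or an alpha. The superiority item beside it in each document does tie its figures to a look and an alpha: power 0.81 for 65% to 32.5%, with 0.0002 "for boundaries for the initial interim analysis when 200 children have been followed to completion", and 0.85 for 65% to 40% with 400 children at 0.012.

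The looks come "after approximately 1/3 (200 subjects) and 2/3 (400 subjects) of the total required patients have completed their primary outcome". A later item in 6.2 confirms the per-arm size: "With 200 subjects per group at a second early stopping review". The only alphas given for the primary endpoint are "0.0002, 0.012, and 0.038) in order to achieve an overall" level of 0.05. SAP 2.3 treats death/BPD as both an efficacy and a safety endpoint and says comparisons on it are two-sided. No separate boundary for harm appears in either document.

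On multiples, Protocol 6.1.1 says: "We have inflated the estimate by 1.12 to allow for twins and multiples to be randomized together". Protocol 6.2 and SAP 4 use a GEE at the interim looks for the same reason.

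**The concern.** Protocol 6.2 gives the reason for interim testing: "Since neonatal safety is a consideration in this study, we have chosen to use a group sequential design". The figure for detecting harm is therefore one that the DSMC and IRBs may rely on. An unlabelled 0.8 can be read as applying to interim monitoring in general, although power differs roughly ninefold between the two looks. The stated interim powers also appear to leave out the allowance for multiples that the plan makes in its sample size and in its interim test. If so, they are not on the same footing as the final design.

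**Working it through.** **Inputs.** Control 65%, SI 80% (Protocol 6.2(2)). Per-arm n of 100, 200 and 300 at the two looks and the final analysis (Protocol 6.2, 6.1.1; 1:1 allocation in 4.4.4). Two-sided alphas 0.0002, 0.012 and 0.038, giving z = 3.719, 2.512 and 2.075. Multiples are allowed for by dividing n by 1.12 (Protocol 6.1.1). Loss to follow-up is taken as nil, as 6.1.1 expects.

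**Formula** (two proportions, pooled variance under the null):

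power = Φ[(d√n − z·s0)/s1], where d = |p1 − p2|, s0 = √(2p̄(1 − p̄)) and s1 = √(p1(1 − p1) + p2(1 − p2)).

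**Anchor.** For 65% against 52.5%, n = 263 and alpha 0.038: (2.027 − 1.445)/0.691 = 0.844, so power is 0.80. This reproduces the main sample size, so the method matches the plan's.

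**The stated 0.8.** For 65% against 80%: p̄ = 0.725, s0 = 0.6315, s1 = 0.6225.

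- Look 2, n = 200: (0.15 × 14.142 − 2.512 × 0.6315)/0.6225 = (2.121 − 1.586)/0.6225 = 0.859. Power 0.805, which is the plan's figure.
- Look 2, n = 200/1.12 = 178.6: (2.005 − 1.586)/0.6225 = 0.672. Power 0.749.
- Look 1, n = 100: (1.500 − 2.348)/0.6225 = −1.363. Power 0.086.
- Look 1, n = 100/1.12 = 89.3: (1.417 − 2.348)/0.6225 = −1.496. Power 0.067.
- Final, n = 300: power 0.981. With n = 267.9: power 0.967.

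The choice of test changes little. Without the factor, unpooled, logit, arcsine, continuity-corrected, exact chi-square and Fisher versions give 0.77 to 0.81 at look 2 and 0.06 to 0.10 at look 1. Reaching 80% power at alpha 0.0002 would take 367 per arm, more than the trial's 300.

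**Why look 1 is so low.** Keep n = 100 and relax alpha: at 0.012 power is 0.44, and at 0.05 it is 0.66 (0.61 with the factor). The small sample alone holds power to about two thirds. The 0.0002 boundary takes it from there to below 0.1.

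**Neighbouring superiority figures, same formula.**

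| Scenario | Stated | No factor | With 1.12 |
|---|---|---|---|
| 65% to 32.5%, 200 infants, 0.0002 | 0.81 | 0.824 | 0.746 |
| 65% to 40%, 400 infants, 0.012 | 0.85 | 0.995 | 0.989 |

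The 0.85 is reproduced by 100 per arm at 0.012: (2.500 − 1.774)/0.684 = 1.062, power 0.856. It matches 200 infants in total, not the 400 that the text names.

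**Sensitivity to the factor.** The documents give neither the share of multiples nor their correlation. If the design effect were 1.05 to 1.20 (an assumed range), harm power would be 0.78 to 0.71 at look 2 and 0.08 to 0.06 at look 1.

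**The case against.** The 0.8 is not a miscalculation. It reproduces at look 2, and the sentence itself opens by calling power limited. Section 6.2 adds that early stopping is unlikely unless the effect is clearly better or worse. This stands: for the harm figure, the defect is a missing label and a missing factor. But 0.8 is a conventional level of adequate power, and nothing in the sentence tells a reader that the first-look value is below 0.1.

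A reader might infer that the DSMC is blind to harm before 400 infants, or that a harmful maneuver would simply run on until then. The documents do not support that. Air leak and related SAEs are compared at 100, 200 and 400 infants against a doubling of risk. SAEs, including deaths within 48 hours, go to the DSMC within 72 hours, and safety stopping rests largely on descriptive data. These routes do not formally test later death or BPD, so they do not replace the missing figure.

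A reader might also infer that the 0.8 holds at look 2 alone, or that the boundary by itself explains the low look-1 power. Final-analysis power is 0.97 to 0.98, and sample size contributes at look 1.

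The inferiority item names no alpha. That harm shares the 0.0002 boundary is inferred from the two-sided statement in SAP 2.3 and the single alpha set. Using the same alphas one-sided would give 0.12 at look 1 (0.09 with the factor) and 0.87 at look 2 (0.82), so the look-1 conclusion would not change.

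Finally, a symmetric two-sided O'Brien-Fleming boundary is a legitimate design. The documents give no ground for calling it an error.

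**Conclusion.** The point holds as one of labelling and consistency. The stated harm power is a second-look figure that ignores multiples. On the plan's own factor it is about 0.75, some 5 points lower, and at the first look about 0.07. The first-look superiority figure falls by about 6 points (0.81 to 0.75). The second-look superiority figure is understated by about 14 points (0.85 against 0.99) and is the largest numerical discrepancy of the three.

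This rests on 1:1 allocation, complete outcomes, harm sharing the two-sided alphas, and 1.12 as an adequate design effect. The last is approximate, but the look-1 conclusion does not depend on it. The figures are probabilities of crossing the formal death/BPD boundary at a given look. They do not describe the whole of the safety monitoring, and they do not show that the boundary is wrong.

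**What to change.** In Protocol 6.2 and SAP section 4, restate interim power by look and alpha, with the 1.12 factor, and note that the values are approximate:

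- Harm, 65% to 80%: about 0.07 at 200 infants (alpha 0.0002) and about 0.75 at 400 (alpha 0.012).
- Superiority, 65% to 32.5%, at 200 infants: about 0.75 in place of 0.81.
- Superiority, 65% to 40%, at 400 infants: about 0.99 in place of 0.85.

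Say explicitly that the two-sided alphas apply in the harm direction too, if that is the intention. The cost is wording only: sample size, alpha and conduct do not change.

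As an option for the sponsor and DSMC, not a required correction, a looser non-binding harm boundary could be considered. For illustration, one-sided 0.025 at each interim look would give harm power of 0.61 to 0.66 at look 1 and 0.89 to 0.92 at look 2, and would spend no efficacy alpha. It would raise the chance of a false harm signal over the two looks from about 0.6% to about 4%. That is a trade-off for them to judge.

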6.1.2. Methods of Analysis

The proposed study is a two-arm parallel design of two alternative courses of treatment. A conventional “as-randomized” analysis (or “intention-to-treat” analysis) will estimate whether the

experimental therapy is superior to conventional therapy in avoiding treatment failure, and is at least as good as conventional therapy in avoiding adverse events.

SAS will be used for secondary data management and descriptive statistics. SAS datasets will be downloaded at least weekly from the study database for analysis. Graphics will be prepared using Stata v11 (or later) (Stata Corp, San Antonio TX, 2009) and the R programming package (The R Foundation for Statistical Computing, Vienna, Austria, 2011). Analyses will be implemented in SAS.

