2.3 Study Endpoints

The primary endpoint for this study is both an efficacy and safety endpoint. Improved death / BPD rates suggest efficacy, while worse rates suggest a safety problem. As such, all comparisons are inherently two-sided. Interim and final analyses present the classic spectrum of decisions: superiority, non-inferiority, and inferiority.

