All of the standard reports described in the previous section will be provided to the DSMC with this analysis. Additional measures to be considered at the interim analysis include baseline clinical factors and adverse events. The study population for all of the analyses provided to the DSMC is the intent-to-treat population, including all participants and time points for which data have been entered and verified in the study database. A summary of the analyses to be included in the interim report is outlined below. Additional details of the statistical methods to be used are given in the next section regarding the final analysis.

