5. FINAL DATA ANALYSIS UPON COMPLETION OF TRIAL

Upon completion of the primary outcome at 36 weeks PMA, after all data has been entered in the database and query resolution is complete, the primary statistical analysis and description of the data will be performed. The final analysis for the 22-26 month cGA secondary outcomes will be completed separately, after that data has been entered in the database and cleaned. The staff biostatistician under the direction of the faculty biostatisticians will produce a final report outlining all analyses and interpretation of the results. This report will be used as the basis of the primary manuscript to be prepared for publication. Details of the analyses and statistical methods to be included in the final report are outlined below. All statistical tests described below will be conducted using a two-sided level of significance.

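### The 80% power quoted for non-inferior efficacy at the second interim look has no margin behind it and matches a superiority calculation; SAP 2.3 also names non-inferiority as a final decision without a rule

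*Protocol*

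**What the plan says.** Protocol 6.2, item (4)(a), and the parallel item in SAP 4 deal with stopping when safety is worse but efficacy is not. For 200 infants per arm and alpha 0.012 they state that the "observed risk in the experimental group would have to be at most 0.5 (risk of death and BPD) to have 80% power". The power is named as "to have 80% power to show non-inferior efficacy". The sentence gives no margin, control risk or sidedness. Item (4)(b) then says that a stop for non-inferior efficacy with better safety would need a large observed improvement.

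SAP 2.3 goes further: "Interim and final analyses present the classic spectrum of decisions: superiority, non-inferiority, and inferiority". The same section says that "all comparisons are inherently two-sided". SAP 5 repeats this for the final analysis ("All statistical tests described below will be conducted using a two-sided level of significance"), and SAP 4 points the interim report to the same methods ("Additional details of the statistical methods to be used are given in the next section regarding the final analysis").

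The other primary-endpoint statements concern superiority. Protocol 6.1.1 says "In order to detect an absolute risk reduction of 12.5%, 263 subjects per treatment arm are required", from a control rate of 65% at alpha 0.038. Protocol 6.1.2 asks whether the "experimental therapy is superior to conventional therapy in avoiding treatment failure". The four stopping comparisons listed in SAP 4 are superiority, futility, inferiority and safety. SAP 5.4.3 gives only a p-value boundary.

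**The concern.** Non-inferiority power is undefined until a margin is fixed, and neither document fixes one. A DSMC member who reads the sentence cannot tell which test the 80% describes. The sentence also attaches power to an observed risk, whereas power is a function of true risks.

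The more practical issue is at the end of the trial. SAP 2.3 offers non-inferiority as a final conclusion for death or BPD, but the analysis section has no margin and no confidence-interval rule. If the primary comparison is not significant, the wording invites a non-inferior label that non-significance alone cannot support.

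**Working it through.** **Inputs.** 200 per arm, alpha 0.012, experimental risk 0.50 (item (4)(a)). Control risk 0.65 is an assumption carried over from Protocol 6.1.1, because item (4)(a) does not state it.

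**Which convention do the neighbouring figures follow?** Pooled-variance test of two proportions:

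power = Φ[(|d| − z·SE0)/SE1], with SE0 = √(2p̄(1−p̄)/n) and SE1 = √((pC(1−pC) + pE(1−pE))/n).

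- Sample size, 65% vs 52.5%, 263 per arm, alpha 0.038 two-sided (z = 2.075): SE0 = 0.0429, SE1 = 0.0426, (0.125 − 0.0891)/0.0426 = 0.84, power 80.1%. One-sided it would be 87.4%.
- Inferiority item, 65% vs 80%, stated 0.8. Taking 200 per arm and alpha 0.012, which that item does not restate: 80.5% two-sided, 86.8% one-sided.
- First look, 65% vs 32.5%, 100 per arm, alpha 0.0002, stated 0.81: 82.4% two-sided, 86.8% one-sided.

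These three fit a two-sided calculation better. The second-look example (65% to 40%, stated 0.85) fits neither; it gives over 99% both ways.

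**The figure in question, 65% vs 50%.** p̄ = 0.575, SE0 = √(2 × 0.575 × 0.425/200) = 0.0494, SE1 = √((0.2275 + 0.25)/200) = 0.0489.

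- Two-sided, z = 2.512: (0.15 − 0.1242)/0.0489 = 0.53, power 70.1%.
- One-sided, z = 2.257: (0.15 − 0.1116)/0.0489 = 0.79, power 78.4%.
- With the 1.12 multiples factor, n = 200/1.12 = 178.6: 64.0% two-sided, 73.1% one-sided.
- True experimental risk needed for 80% power: 48.4% two-sided, 49.7% one-sided. Both print as 0.5 to one decimal.

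Two-sided power against a true 50%, by control risk: 31% at 60%, 70% at 65%, 80% at 66.5%, and 88% at 68% (the rate cited in Protocol 1.1).

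**Could it be a non-inferiority power?** With margin M, power = Φ[(M + pC − pE)/SE1 − z]. At one-sided alpha 0.012:

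| True risks | Power by margin |
|---|---|
| 65% vs 50% | 79% (M = 0), 97% (5 points), 99.8% (10 points) |
| 65% vs 65% | 11% (5 points), 44% (10 points), 81% (15 points) |

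At 65% vs 50% the margin that returns exactly 80% is 0.1 points, which is in effect zero. Equal risks with a 15-point margin also come near 80%. But that test would pass an observed experimental risk up to about 0.65 + 0.15 − 2.257 × 0.0477 = 0.69, which is not a condition of at most 0.5.

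**Read literally as observed rates.** Observed 65% vs 50% gives z = 0.15/0.0494 = 3.03, p = 0.0024, already past 0.012. With control observed at 65%, the boundary is crossed at about 52.6%. An observed 50% crosses it only if control is observed at about 62.5% or more. These figures ignore multiples.

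**What a null result could show.** With both arms at 65% and 300 per arm, taking 0.038 as the final level, the half-width of the risk-difference interval is 2.075 × √(2 × 0.65 × 0.35/300) = 0.081, about 8 points (8.6 with the 1.12 factor).

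**The case against.** The sentence is an illustration inside a safety item. Both documents leave that stop mainly to descriptive judgement and review of adverse events, and no boundary uses the 0.5. This stands: the interim is not without guidance, and the observed-for-true wording may be only a slip. It does not reach SAP 2.3, which carries non-inferiority to the final analysis.

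The calculation behind the 80% is not shown and the control rate is not in the sentence, so calling it a superiority calculation is an inference. This also stands, and the claim here is only that the figure matches one.

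A reader might infer that the sentence is one-sided and so conflicts with the SAP's two-sided rule, since 78% is nearer to 80% than 70% is. The documents do not support this. The two-sided solution of 48.4% also prints as 0.5, and the adjacent inferiority figure and the sample size both reproduce two-sided. For the same reason the 80% is not shown to be an arithmetic error.

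Protocol 6.1.2 also aims to show that the intervention is no worse on adverse events. That is non-inferiority language, but about a separate safety comparison. It supplies no margin for death or BPD.

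**Conclusion.** The point holds in a limited form. A power quoted in the DSMC's stopping guidance is labelled non-inferiority although no margin exists. On the assumed 65% control risk it matches a zero-margin superiority calculation. For a true risk of exactly 50%, two-sided power is about 70%, or about 64% allowing for multiples. The result is sensitive to the assumed control risk, as the range above shows.

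SAP 2.3 separately names a final decision on the primary endpoint for which there are only p-value boundaries. With equal arms at 65%, the final interval would still extend about 8 points either way, so a non-significant result would not by itself establish non-inferiority.

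The impact is minor. The primary test, the sample size and the boundaries are unaffected, and interim safety stopping remains largely the DSMC's judgement.

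**What to change.** In both Protocol 6.2 and SAP 4, item (4)(a), delete the sentence with the 0.5 and the 80%, or restate it as superiority at a true risk, for example:

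> With 200 infants per arm at the second interim analysis and two-sided alpha 0.012, power is about 70% (about 64% allowing for the 1.12 multiples factor) to detect a reduction in true risk from 65% to 50%.

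Remove non-inferiority for the primary endpoint from SAP 2.3 and bring the efficacy wording in (4)(a) and (4)(b) into line. Leave the adverse-event aim in Protocol 6.1.2 as a distinct safety comparison. For a non-significant primary result, report the risk difference with an interval that matches the final boundary, and make no non-inferiority claim.

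If the sponsor wants to keep non-inferiority, it must prespecify the margin, sidedness and interval rule, and recompute the power from them.

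The cost is wording in two documents. The sponsor gives up the non-inferiority label unless it justifies a margin, and the stated power becomes less favourable.
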